# 8.2.6 Health Utilities Index

The Health Utilities Index (HUI) is a rating scale used to measure general health status and health-related quality of life. The HUI questionnaires are designed to map onto 2 classification systems, HUI-2 and HUI-3, capable of measuring 24,000 and 972,000 unique health states, respectively. The HUI classifications measure a range of health domains with examples including sensation, mobility, pain, cognition, ambulation, and emotion (Horsman et al, 2003).

#### 8.3 Safety Assessments

Planned time points for all safety assessments are provided in the Schedule of Assessments (Table 2).

For the assessments described below, when multiple procedures are scheduled on the same visit, the following chronology of events should be adhered to, where possible:

- ECGs, obtain prior to vital sign measurements
- Vital sign measurements, obtain prior to procurement of blood specimens
- Blood specimen collection
- Other procedures: all other procedures may be obtained before or after blood specimen collection

# 8.3.1 *Physical and Neurological Examinations*

A complete physical examination will consist of measurement of height (screening only) and weight and a review of the following body systems: head, ears, eyes, nose, mouth, skin, heart and lung examinations, lymph nodes, gastrointestinal, genitourinary, and musculoskeletal systems. If the investigator/designee is unable to perform a genitourinary examination, special attention will be given to the genitourinary medical history. A prior record (within 12 months) of a recent genitourinary examination from a gynecologist or family doctor can substitute for a genitourinary examination.

A full neurological examination will include an assessment of the subject's mental status (level of consciousness, orientation, speech, memory, etc.), cranial nerves, motor (muscle appearance, tone, strength and reflexes), sensation (including Romberg sign), coordination, and gait.

Height will be measured at screening only.

The following guidelines will aid in the standardization of body weight measurements:

• The same scale should be used to weigh a given subject each time, if possible

- Scales should be calibrated and reliable; scales should be at zero just prior to each subject's weigh-in session
- A subject should void prior to being weighed and be minimally clothed (ie, no shoes or heavy overgarments)
- Weight should be recorded before a subject's meal and at approximately the same time at each visit

The investigator (or designee) is responsible for performing the physical and neurological examinations. If the appointed designee is to perform these examinations, he or she must be permitted by local regulations and his or her name must be included on the delegation of authority log. Whenever possible, the same individual should perform all physical and neurological examinations.

Any condition present at the post-treatment physical and neurological examinations that was not present at the baseline examination should be documented as an AE and followed to a satisfactory conclusion.

# 8.3.2 Vital Sign Measurements

Vital sign measurements will include body temperature, respiratory rate, systolic blood pressure, diastolic blood pressure, and heart rate.

Vital signs will be measured with the subject in a sitting/semi-recumbent position after 5 minutes rest and will include temperature, systolic and diastolic blood pressure, and heart rate.

A properly sized and calibrated blood pressure cuff will be used to measure blood pressure each time. The use of an automated device for measuring blood pressure and heart rate is acceptable, although, when done manually, heart rate will be measured in the brachial/radial artery for at least 30 seconds. When the timing of these measurements coincides with a blood collection, blood pressure and heart rate should be obtained prior to the nominal time of the blood collection.

Body temperature will be measured with either an oral (temperature taken at floor of the mouth) or tympanic thermometer. The same method (ie, oral or tympanic) must be used for all measurements for each individual subject and should be the same for all subjects at each investigational site.

# 8.3.3 Electrocardiograms

Electrocardiogram recordings will be obtained after the subject has been supine and at rest for at least 5 minutes. Additional 12-lead ECGs may be obtained at the investigator's discretion and should always be obtained in the event of early termination. The ECG results will be evaluated at the investigational site to determine the subject's eligibility and to monitor safety during the trial. The investigator (or qualified designee) will

review, sign, and date each ECG reading, noting whether or not any abnormal results are of clinical significance. Any clinically relevant changes occurring during the trial will be recorded in the AE section of the eCRF. The ECG will be repeated if any results are considered to be clinically significant. A central ECG service will be used for reading all ECGs in order to standardize interpretations for the safety analysis.

If, during screening, an abnormal ECG finding is deemed medically significant according to the investigator's judgment (impacting the safety of the subject or the interpretation of the trial results) or meets an exclusion criterion (see Section 5.2), the subject should be excluded from the trial. At screening, triplicate ECG recordings should be taken approximately 1 minute apart. The central ECG service will provide the QT interval corrections based on Fridericia's formula (QTcF) for the 3 screening ECGs. A mean QTcF >450 msec as assessed by the central reader from the screening triplicate ECGs will be exclusionary.

Exclusion criteria for screening do not apply as mandatory discontinuation criteria for subjects who are already randomized. A repeat ECG should be performed to confirm any clinically significant abnormality that is identified in a randomized subject during the treatment period (which will be confirmed by central service read) and, in these cases, the medical monitor should be consulted on the appropriateness of the subject continuing in the trial.

# 8.3.4 Clinical Safety Laboratory Assessments

See Section 10.2 (Appendix 2) for the list of clinical laboratory tests to be performed and to the Schedule of Assessments (Table 2) for the timing and frequency.

The investigator must review the laboratory report, document this review, and record any clinically relevant changes occurring during the trial in the AE section of the eCRF. The laboratory reports must be filed with the source documents. Clinically significant abnormal laboratory findings are those which are not associated with the underlying disease, unless judged by the investigator to be more severe than expected for the subject's condition.

All laboratory tests with values considered clinically significantly abnormal during participation in the trial should be repeated until the values return to normal or baseline or are no longer considered clinically significant by the investigator or medical monitor.

If such values do not return to normal/baseline within a period of time judged reasonable by the investigator, the etiology should be identified and the medical monitor notified.

All protocol-required laboratory assessments, as defined in Section 10.2 (Appendix 2), must be conducted in accordance with the laboratory manual and the Schedule of Assessments (Table 2).

# 8.3.5 Modified Clinical Institute Withdrawal Assessment – Benzodiazepines

The modified Clinical Institute Withdrawal Assessment – Benzodiazepines (mCIWA-B) is a sensitive instrument to measure withdrawal under conditions where there is a taper of medication (rather than abrupt discontinuation). It consists of 17-items that monitor the type and severity of BZD withdrawal symptoms such as irritability, fatigue, appetite, and sleeplessness (Busto et al, 1989). The clinician-observed assessments of sweating, restlessness (pacing), and tremor that are included in the overall version have been removed from this modified version. The total score ranges from 1 to 68 with higher scores indicating more severe withdrawal.

# 8.3.6 Suicidal Ideation and Behavior Risk Monitoring

Suicidality will be monitored during the trial using the Columbia – Suicide Severity Rating Scale (C-SSRS). This semi-structured interview was originally developed to evaluate the link between antidepressants and suicidal behavior and ideation in youth and AEs from pediatric clinical trials (Posner et al, 2011). It was designed to quantify the severity of suicidal ideation and behavior. Trial personnel administering the C-SSRS must have completed the appropriate training and have valid certification. Training on the scale will be provided via the sponsor or designee.

This trial will use the "Baseline/Screening" and "Since Last Visit" versions of the scale. The "Baseline/Screening" version, which assesses the lifetime experience of the subject with suicide events and suicidal ideation and the occurrence of suicide events or ideation within a specified time period prior to entry into the trial, will be completed for all subjects at screening to determine eligibility and confirmed at baseline. Any subject with active suicidal ideation or suicidal behaviors within the last 6 months, suicidal behaviors within the last 2 years, or who in the clinical judgment of the investigator presents a serious risk of suicide should be excluded from the trial (see Section 5.2).

The "Since Last Visit" C-SSRS form will be completed at all visits after screening and Visit 1. The investigator will review the results of the "Since Last Visit" C-SSRS during the trial to determine whether it is safe for the subject to continue in the trial. If a subject demonstrates potential suicidal ideation associated with actual intent or method or plan as indicated by "YES" answers on item 4 or 5 of the C-SSRS, the investigator will need to evaluate whether a risk assessment by a qualified mental health professional (MHP, or the investigator alone if the investigator is a qualified MHP) is needed and whether the subject should continue in the trial or be discontinued.

# 8.4 Adverse Events and Serious Adverse Events

The definitions of an AE or SAE can be found in Section 10.3 (Appendix 3).

Adverse events will be reported by the subject (or, when appropriate, by a caregiver, surrogate, or the subject's legally authorized representative).

The investigator and any qualified designees are responsible for detecting, documenting, and recording events that meet the definition of an AE or SAE and remain responsible for following up AEs that are serious, considered related to the IMP or trial procedures, or that caused the subject to discontinue IMP (see Section 7)

# 8.4.1 Time Period and Frequency for Collecting AE and SAE Information

All AEs and SAEs will be collected from the signing of the ICF through the subject's last visit at the time points specified in the Schedule of Assessments (Table 2).

Adverse events that begin before the start of IMP but after obtaining informed consent will be recorded and categorized as pretreatment AEs. Any AE occurring after initiation of IMP are defined as treatment-emergent AEs (TEAEs).

All SAEs will be recorded and reported to the medical monitor immediately and under no circumstance should this exceed 24 hours, as indicated in Section 10.3 (Appendix 3). The investigator will submit any updated SAE data to the medical monitor within 24 hours of it being available.

Investigators are not obligated to actively seek AE or SAE after conclusion of the trial participation. However, if the investigator learns of any SAE, including a death, at any time after a subject has been discharged from the trial, and he/she considers the event to be reasonably related to the IMP or trial participation, the investigator must promptly notify the sponsor.

# 8.4.2 Method of Detecting AEs and SAEs

The method of recording, evaluating, and assessing causality of AE and SAE and the procedures for completing and transmitting SAE reports are provided in Section 10.3 (Appendix 3).

Care will be taken not to introduce bias when detecting AEs and/or SAEs. Open-ended and nonleading verbal questioning of the subject is the preferred method to inquire about AE occurrences.

# 8.4.3 Follow-up of AEs and SAEs

After the initial AE/SAE report, the investigator is required to proactively follow each subject at subsequent visits/contacts. All SAEs will be followed until resolution, stabilization, the event is otherwise explained, or the subject is lost to follow-up (as defined in Section 7.5). Further information on follow-up procedures is given in Section 10.3 (Appendix 3).

# 8.4.4 Regulatory Reporting Requirements for SAEs

Prompt notification by the investigator to the medical monitor of a SAE is essential so that legal obligations and ethical responsibilities towards the safety of subjects and the safety of an IMP under clinical investigation are met.

The sponsor has a legal responsibility to notify both the local regulatory authority and other regulatory agencies about the safety of an IMP under clinical investigation. The sponsor will comply with country-specific regulatory requirements relating to safety reporting to the regulatory authority, IRB/ IEC, and investigators.

Investigator safety reports must be prepared for suspected unexpected serious adverse reactions (SUSARs) according to local regulatory requirements and sponsor policy and forwarded to investigators as necessary.

An investigator who receives an investigator safety report describing a SAE or other specific safety information (eg, summary or listing of SAEs) from the sponsor will review, acknowledge, and then file it along with the Investigator's Brochure and will notify the IRB/IEC, if appropriate according to local requirements.

# 8.4.5 Pregnancy

Details of all pregnancies in female subjects and female partners of male subjects will be collected after the start of IMP and until the final contact on Day 120.

If a pregnancy is reported, the investigator should inform the medical monitor within 24 hours of learning of the pregnancy and should follow the procedures outlined in Section 10.4 (Appendix 4).

Abnormal pregnancy outcomes (eg, spontaneous abortion, fetal death, stillbirth, congenital anomalies, ectopic pregnancy) are considered SAEs.

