AED = anti-epileptic drug; BID = twice daily; BZD = benzodiazepine; CGI-I = Clinical Global Impression-Improvement; CGI-S = Clinical Global Impression – Severity of Symptoms; C-SSRS = Columbia-Suicide Severity Rating Scale; CT = computed tomography; ECG = electrocardiogram; ET = Early Termination; HBV = hepatitis B virus; HCG = human chorionic gonadotropin; HCV = hepatitis C virus; HIV = human immunodeficiency virus; ICF = informed consent form; IMP = investigational medicinal product; mCIWA-B = Modified Clinical Institute Withdrawal Assessment – Benzodiazepines; MRI = magnetic resonance imaging; PGIC = Patient Global Impression of Change; PK = pharmacokinetic; QOLIE-31 = Quality of Life in Epilepsy-31; SIF/DRF = Seizure Identification and Diagnostic Review Form; TESC = The Epilepsy Study Consortium.

- a. Individual sites may require subjects to have COVID-19 testing done prior to randomization. COVID-19 testing may be performed after randomization per the investigator's discretion.
- b. Contact with subject via phone call or other means of communication to check on their status.
- c. In the event that a subject is unable to attend a clinic visit in person due to restrictions related to COVID-19, this visit may be completed remotely. Please refer to the Trial Operations Manual for further instructions related to remote visits.
- d. At Visit 4, the investigator will evaluate the subject's eligibility to continue treatment with CVL-865 in the open-label extension trial CVL-865-SZ-002. If the investigator determines the subject is eligible for the trial, he/she will discuss with the subject if they would like to continue into Trial CVL-865-SZ-002. If the investigator determines the subject is eligible and the subject agrees to continue participation in Trial CVL-865-SZ-002, consent will be obtained and unique procedures for Visit 1 of Trial CVL-865-SZ-002 will be completed. Subjects who do not continue into Trial CVL-865-SZ-002 will begin the Taper Phase.

- e. Subjects who require early termination should begin the Taper Period at the time the decision is made to discontinue. All indicated procedures should be performed per protocol. If a subject discontinues early and it is inadvisable for them to taper IMP (after agreement from medical monitor), the subject should complete Visit 6 assessments approximately 30 days following the last dose of IMP.

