#### Treatment Period:

Subjects who satisfy all inclusion/exclusion criteria and thus are eligible for the trial will be randomized to 1 of 3 treatment arms at Visit 1.

The daily dosing schedule will start at Day 1 with a 2-week Titration Phase during which time the subject's dose will be increased in a blinded fashion up the randomized dose level (CVL-865 25 mg BID, CVL-865 7.5 mg BID, or placebo). In the high-dose group, CVL-865 will be administered as

during the Titration Phase, and then 25 mg BID during the 8-week Maintenance Phase. In the low-dose group, CVL-865 will be administered as

during the Titration Phase, and then 7.5 mg BID

during the 8-week Maintenance Phase.

At the completion of the Maintenance Phase, the investigator will evaluate the subject's eligibility to continue treatment with CVL-865 in the open-label extension trial CVL-865-SZ-002. If the investigator determines the subject is eligible for the trial, he/she will discuss with the subject if they would like to continue into Trial CVL-865-SZ-002. If the investigator determines the subject is eligible and the subject agrees to continue participation in Trial CVL-865-SZ-002, consent will be obtained and unique procedures for Visit 1 of Trial CVL-865-SZ-002 will be completed.

For subjects who do not continue into Trial CVL-865-SZ-002, following the Maintenance Phase, the dose will be gradually decreased over a 3-week Taper Phase.

A summary of the dosing schedule is provided below.

	Titratio	on Phase	Maintenance Phase	Taper Phase a				
Dose Initiation			Day 15	Day 78	Day 85	Day 92		
Duration	2 w	eeks	8 weeks					
CVL-865 7.5 mg BID			7.5 mg BID	5 mg BID	5 mg BID	2.5 mg BID		
CVL-865 25 mg BID			25 mg BID	17.5 mg BID	10 mg BID	5 mg BID		
Placebo	Placebo	Placebo	Placebo	Placebo	Placebo	Placebo		

Table 4 Dosing Schedule

Abbreviations: BID = twice daily.

a Only for subjects who do not continue treatment with CVL-865 in Trial CVL-865-SZ-002.

Subjects are to continue the same concurrent AEDs at the same dosages administered during the Treatment Period. If a subject has a VNS, DBS, or RNS, the settings must remain stable throughout the Treatment Period.

Subjects will continue to record all seizures and the presence or absence of all seizure types experienced in the eDiary for each day during the Treatment Period.

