## 4.4 Definition of Completed Subject

Subjects continuing treatment with CVL-865-SZ-001 in the open-label extension trial are considered to have completed this trial if he/she has completed the Maintenance Phase of the trial (ie, completed Visit 4) as shown in the Schedule of Assessments.

Subjects not continuing in the open-label extension trial, are considered to have completed this trial if he/she has completed all phases of the trial including the last scheduled procedure (Day 120 phone contact) shown in the Schedule of Assessments.

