9.	A female subject of childbearing potential (see Section 10.4, Appendix 4) who is sexually active with a nonsterilized male partner must agree to use a highly effective method of contraception (see Section 10.4, Appendix 4) from signing of informed consent throughout the duration of the study and for 30 days post last dose.
	A male subject with a pregnant or a nonpregnant partner of childbearing potential must agree to use condom during treatment and until the end of relevant systemic exposure in the male subject for 94 days following the last dose with IMP.
10.	Capable of giving signed informed consent as described in Section 10.1.3 (Appendix 1), which includes compliance with the requirements and restrictions listed in the ICF and in this protocol.
11.	Ability, in the opinion of the investigator, to understand the nature of the trial and comply with protocol requirements, including the prescribed dosage regimens, scheduled visits, laboratory tests, and other trial procedures.

Abbreviations: AED = anti-epileptic drug; BMI = body mass index; CT = computed tomography; DBS = deep brain stimulator; EEG = electroencephalogram; ICF = informed consent form; ILAE = International League Against Epilepsy; IMP = investigational medicinal product; MRI = magnetic resonance imaging; RNS = responsive neurostimulator; TESC = The Epilepsy Study Consortium; VNS = vagus nerve stimulator

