# 10.4.2 Collection of Pregnancy Information

#### 10.4.2.1 Male subjects with partners who become pregnant

- The investigator will attempt to collect pregnancy information on any male subject's female partner who becomes pregnant while the male subject is in this trial. This applies only to male subjects who receive IMP.
- After obtaining the necessary signed informed consent from the pregnant female partner directly, the investigator will record pregnancy information on the appropriate form and submit it to the sponsor within 24 hours of learning of the partner's pregnancy. The female partner will also be followed to determine the outcome of the pregnancy. Information on the status of the mother and child will be forwarded to the sponsor. Generally, the follow-up will be no longer than 6 to 8 weeks following the estimated delivery date. Any termination of the pregnancy will be reported regardless of fetal status (presence or absence of anomalies) or indication for the procedure.

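### For men who complete the taper and do not enter the extension, partner pregnancies go uncollected for about 65–66 of the 94 post-dose days in which condoms are required

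*Protocol*

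**What the plan says.** **Contraception.** Criterion 9 (Protocol 5.1) sets different post-dose periods for the two sexes. Women of childbearing potential must use highly effective contraception "throughout the duration of the study and for 30 days post last dose". Men must use condoms during treatment and "until the end of relevant systemic exposure in the male subject for 94 days following the last dose with IMP".

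**Collection.** Section 8.4.5 has one end date for both sexes: pregnancy details in "female partners of male subjects will be collected after the start of IMP and until the final contact on Day 120". For men, Section 10.4.2.1 (Appendix 4) covers a partner "who becomes pregnant while the male subject is in this trial". Such a pregnancy, once the partner consents, is followed to outcome: "Generally, the follow-up will be no longer than 6 to 8 weeks following the estimated delivery date".

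**Timing of the last dose and last contact.** For men not entering the extension, Section 4.1 says "the dose will be gradually decreased over a 3-week Taper Phase", followed by a 4-week follow-up; Section 4.4 places the last scheduled procedure at Day 120. For early stoppers in whom a taper is inadvisable, footnote e of the Schedule of Assessments says "the subject should complete Visit 6 assessments approximately 30 days following the last dose of IMP", and Section 7.3 agrees.

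**After the trial.** Section 8.4.5 classes abnormal pregnancy outcomes as SAEs. Sections 8.4.1 and 10.3.3 require investigators to report post-trial SAEs that they learn of and consider related, but not to look for them. No other section of the protocol, and nothing in the SAP, extends partner-pregnancy collection to 94 days.

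**The concern.** Section 2.3 names fetal toxicity as an important potential risk and says it will be limited by contraception and pregnancy testing. Testing applies to women in the trial, so for male subjects the condom rule is the only one of those two measures that operates. Criterion 9 itself ties the 94 days to relevant systemic exposure. A sponsor that wants condoms used for that long would be expected to want to know about conceptions in the same period.

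The Day 120 contact nearly matches the women's post-dose window but covers less than a third of the men's, and the protocol gives no reason for the difference. At stake is a small amount of reproductive-safety information: a partner pregnancy conceived in the uncovered period would be neither recorded nor followed to outcome unless it led to an abnormal outcome that reached the investigator and was judged related.

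**Working it through.** **Inputs.** Condom period: 94 days after last dose (5.1, criterion 9). End of collection: Day 120 final contact (8.4.5). Visit 4 on Day 71, Visit 5 on Day 92, Visit 6 on Day 120, with a ±3-day window (Schedule of Assessments). Taper 3 weeks, follow-up 4 weeks (4.1). Visit 6 about 30 days after the last dose if there is no taper (7.3 and footnote e).

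**Reproducing the plan's Day 120.** Day 71 + 21 days of taper = Day 92; Day 92 + 28 days of follow-up = Day 120. This matches exactly, and 8 + 13 + 4 = 25 weeks matches the stated maximum duration. The last dose is therefore at about Day 91–92.

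**Formula.** Uncovered days = 94 − (day of final contact − day of last dose).

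| Man not entering the extension | Days covered | Days uncovered |
|---|---|---|
| Completes taper, last dose Day 91 | 120 − 91 = 29 | 94 − 29 = 65 (69%) |
| Completes taper, last dose Day 92 | 120 − 92 = 28 | 94 − 28 = 66 (70%) |
| Stops early, no taper, collection ends at own Visit 6 | 30 | 94 − 30 = 64 (68%) |

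The ±3-day window on Visit 6 widens the taper-completer figures to 62–69 days.

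**Early stoppers if Day 120 is a fixed calendar day.** For a last dose on Day L, the gap is max(0, L + 94 − 120) = max(0, L − 26). Day 71 gives 45, Day 43 gives 17, and Day 26 or earlier gives 0.

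**Early stoppers who taper** (the default in footnote e). The protocol does not state the day of their final contact. If the usual 28-day follow-up applies, the gap is 94 − 28 = 66 days; under a fixed Day 120, the L − 26 rule applies with L the last taper dose.

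**Comparison with women.** For a last dose on Day 91–92, the same contact covers 29 or 28 of their 30 days.

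**Expected number of events.** The documents give no inputs, so these are assumptions: 10–50 active-arm men stop IMP in this trial, and partner pregnancies occur at 2–10 per 100 person-years.
- Low: 10 × 64 / 365.25 = 1.75 person-years; × 0.02 = about 0.04 pregnancies.
- High: 50 × 66 / 365.25 = 9.0 person-years; × 0.10 = about 0.9 pregnancies.

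The high end is generous. It takes half of the 100 planned active-arm subjects and counts every man, although criterion 9 applies only to men whose partner is pregnant or of childbearing potential.

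**The case against.** The strongest reply is that no stated rule is broken. Contraceptive duration and pregnancy collection are separate requirements, and nothing in the documents says they must be equal. The sponsor also did consider the post-trial period: abnormal outcomes are SAEs, and related SAEs learned of later must be reported. Section 10.4.2.2 takes the same passive approach to post-trial pregnancy-related SAEs, although it sits under female subjects and has no counterpart for male subjects' partners. Birth-control methods are reviewed at the Day 99 contact and at Visit 6, and the consent form, which was not available for this review, may already ask men to report later pregnancies. Finally, the SAP is labelled final and describes randomization in the past tense, so an amendment may come too late to matter.

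Most of this stands as a limit on importance. It does not close the gap: the SAE route does not capture uncomplicated pregnancies, and a review of contraceptive methods at Day 120 creates no duty to report a conception in the following two months.

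A reader might infer a larger gap from Table 4, which dates the last taper step from Day 92. If that step lasted a week, the last dose would fall on Day 98 and the gap would be 94 − 22 = 72 days. The rest of the design does not support this. The visit schedule and the SAP's analysis periods both start the taper at Visit 4 (Day 71), and IMP compliance is last scheduled at Visit 5 or early termination. The 72 rests on Table 4's step labels alone.

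**Conclusion.** The mismatch is real and minor. For men who complete the taper and do not continue into CVL-865-SZ-002, about 65–66 of the 94 condom days have no partner-pregnancy collection. This assumes a last dose at Day 91–92 and a final contact on Day 120. For early stoppers without a taper, the figure depends on how 8.4.5 is read. The references to a final contact and to being in the trial favour about 64 days, but a literal Day 120 gives max(0, L − 26). It would be wrong to infer that every man who stops IMP here has a gap of two months or more.

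Two further inferences go beyond the documents. One is that nothing after Day 120 would be captured; the SAE route described above remains. The other is that a fetus could be exposed throughout the gap. The protocol does not derive the 94 days, and its overdose section (8.5) asks for monitoring until the drug is undetectable, with a minimum of only 3 days. The finding concerns unmatched windows and does not show exposure.

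Under the assumptions shown, between zero and one pregnancy would be expected in the uncovered period. Efficacy and power are unaffected. The change is worth considering because it is cheap and concerns a risk the protocol itself names.

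**What to change.** At the next amendment, reword 8.4.5 and 10.4.2.1 so that a partner pregnancy conceived within 94 days of a male subject's last dose in this trial is reportable and followed to outcome under the existing partner-consent procedure. At the final contact, instruct men to report any such pregnancy. Tying the rule to the last dose also removes the ambiguity for early stoppers. Alternatively, state why 94 days of condom use needs only about 30 days of pregnancy collection.

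No visit or test is added. The costs are a passive reporting duty beyond Day 120, outcome follow-up that may run to several weeks after delivery, IRB/IEC approval of the amendment (10.1.1), and re-consent of current subjects if the consent form changes (10.1.3). Some late reports may have to go by paper or telephone once a site's electronic tool is offline (10.3.4). If all men are already more than 94 days past their last dose, the change no longer helps this trial.
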